 Strikingly, 29% of patients receiving organized outreach completed screening within one year. All these patients were not up-to-date with screening at baseline, despite being age-eligible for screening, and having access to care through JPS' medical assistance program for the uninsured. Results of comparisons of the intervention group to the usual care group not receiving organized outreach

Group	Invited, n	Completed Screening, n	Screening Completion Rate
All Outreach Patients	2080	601	29%
FIT	1600	532	33%
Colonoscopy	480	69	14%

were subject of ongoing statistical analyses at time of this grant submission.

- 4 patients with CRCs, and 60 patients with one or more adenomas have been identified. Therefore, our outreach approach has successfully identified patients with CRCs and potentially precancerous polyps.
- The rate of screening completion was two times higher for patients invited to FIT vs. colonoscopy screening. 33% of patients assigned to the FIT invitation completed screening, compared to 14% of patients assigned to the colonoscopy invitation, a 19% absolute difference in screening completion rates. These data demonstrate that screening rates are highly dependent on which screening test is offered. Because test participation in any test is likely to be more closely associated with positive CRC outcomes than which screening test type is completed, our preliminary data support future mailed outreach invitations with FIT, rather than colonoscopy (Table 2). Accordingly, in our expanded outreach program, we will invite patients to complete FIT screening, and use colonoscopy to follow up patients with abnormal tests. This approach has the added advantage of allowing us to offer organized outreach invitations to all eligible uninsured patients not up-to-date with screening (over 20,000), whereas with a colonoscopy based approach we could only offer screening to a small subset of patients due to budget and colonoscopy capacity constraints.

CHALLENGES REMAINING DESPITE PRIOR CPRIT PROGRAM SUCCESS

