Data Sources and Data Tracking. *Our approaches to data acquisition, as well as data tracking have been previously developed and previously used to evaluate CRC screening rates and deliver screening.* The primary data source used to identify patients eligible for our outreach program will be JPS administrative claims database and Epic electronic medical record. At baseline, these data will be queried to identify all 50 to 64 year old patients potentially eligible for program inclusion. Demographic data, such as sex and race/ethnicity, as well as visit data, such as dates of any health system visits and any associated CPT codes with health system visits will be extracted and analyzed to determine which patients are eligible and up-to-date with screening. Data required for inviting patients to screening and tracking follow up, such as names and addresses, will be imported into a tracking database that has been previously developed and tested for this purpose. The tracking database facilitates all day to day program activities and associated data collection. For example, daily, a report is generated of patients who have been mailed FIT, and are due for follow up phone reminders to complete the FIT and return it. The database also allows for updating patient results, such as results of FIT and colonoscopy tests.

Sub-Study Procedures:

A sub-study will be conducted with the goal of identifying strategies that may further increase rates of 1) initial participation in colorectal cancer screening, and 2) follow up of abnormal colorectal cancer screening tests with colonoscopy. This sub-study involves 2 parts:

Part 1) Participants scheduled to receive mailed fecal immunochemical test (FIT) outreach for the first time late in the 2nd year of the study (currently ongoing) will be randomly assigned to receive one of three invitation letters, which vary slightly from one another. These letters represent small, but potentially impactful modifications to our original invitation letters.

All participants randomized to the original \$5 and \$10 incentive groups were enrolled during Year 1 of the study. After the incentive groups reached full enrollment, all new participants received the Version 8, June 29, 2015 11

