Evaluation Aim A) Determine screening rate improvement after expanding screening outreach to all unscreened patients. The denominator population for evaluating baseline and end of Year 3 screening rates will consist of patients meeting the following criteria: 1) Age 50-64, 2) Uninsured, but participants in JPS's medical assistance program for the uninsured, 3) One or more visits to a JPS primary care clinic within a year, 4) Address and phone number on file, 5) No history of CRC or colon resection, 6) Not incarcerated

Thus, the denominator population for our baseline and end of Year 3 follow comparisons of screening rates generally includes patients age-eligible for screening outreach. The numerator for calculation of screening rates will be the number of patients who are up-to-date with screening based on colonoscopy within 10 years, sigmoidoscopy within 5 years, or stool blood test (guaiac FOBT or FIT) within the last year, measured by HEDIS criteria. Thus, the screening rate at baseline and at end of Year 3 will be defined by:

Screeni ng Rate ▪ _	# up-to-date with
	screening

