Secondary analyses. We plan to conduct several secondary analyses. First, we recognize that results from Evaluation Aim A, in which baseline screening rates will be compared to follow up screening rates at year 3, could be confounded by time trends in CRC screening rates, which generally have been increasing over time. Accordingly, we will compare the observed rate of CRC screening in Year 3 to the expected rate of CRC screening based on time trends in screening at JPS. The expected rate will be estimated using the secular trend for CRC screening using annual screening rates for each of the 7 years 2006-2011 prior to start of our prevention program in 2012. All rates will be standardized by gender and age strata (50-54, 55-59, and 60-64 years) to the population distribution of men/women and these age strata for 2012, and a standardized incidence ratio (SIR) will be computed. An SIR greater than 1, with an associated 95% confidence interval that does not cross 1 will be interpreted as evidence to support impact of our outreach intervention beyond time trends in CRC screening rates. We have previously used this approach to assess impact of a University of Texas health plan policy that waived copays for colonoscopy screening on CRC screening rates which began in 2009, in which we compared colonoscopy uptake 2002-2008 to uptake after policy institution⁴⁶.

Version 8, June 29, 2015

Second, to identify factors independently associated with screening outcomes, we will construct several logistic regression models. For example, to identify predictors of initial screening completion, we will create a model using initial screening completion rate as the primary outcome (dependent) variable, and several potential predictors of completion. Predictors considered for model inclusion will include age, sex, race/ethnicity, frequency of primary care visits, exposure to the screening outreach program, and exposure to financial incentives. A similar model will be created with the outcome of programmatic screening as the dependent variable. For these exploratory analyses, 2-sided p values of 0.05 will be considered statistically significant.

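### Aim A's only trend-adjusted rule states neither the trend model nor the interval method, and counts 2006-2011 (six years) as seven

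*Combined protocol and SAP*

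**What the plan says.** Evaluation Aim A compares the baseline screening rate with the rate at the end of Year 3 by an unadjusted chi-square test. The first item under Secondary analyses says that this result "could be confounded by time trends in CRC screening rates, which generally have been increasing over time". The remedy is to compare the observed Year 3 rate with an expected rate taken from the secular trend in "annual screening rates for each of the 7 years 2006-2011 prior to start of our prevention program in 2012". Rates are standardized by sex and three age bands to the 2012 population. The decision rule reads: "An SIR greater than 1, with an associated 95% confidence interval that does not cross 1 will be interpreted as evidence to support", and the claim it supports is "evidence to support impact of our outreach intervention beyond time trends in CRC screening rates".

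The same paragraph says the approach was used before, for a health-plan copay policy, "in which we compared colonoscopy uptake 2002-2008 to uptake after policy institution", and cites a paper for it.

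No form for the trend, extrapolation rule or interval method is stated here or elsewhere in the document. Year 3 has no calendar date. The logistic models that follow list no calendar-time term, and the chart review of cancers attributes cancers, not changes in the screening rate. The SIR rule is therefore the only trend-adjusted analysis for Aim A.

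**The concern.** The expected rate is not observed. It is a projection, three or more years past 2011, of a trend fitted to about six annual points. The conventional SIR interval reflects only the variability of the observed count and takes the expected figure as known. Used that way, it ignores what is likely to be the larger part of the uncertainty. The form of the trend can also move the SIR across 1. With neither choice stated, both could be made after the Year 3 rate is known, and they can decide whether the plan's claim of impact beyond trend is supported.

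Two smaller points add to this. The year count and the year range disagree. The baseline may also include the earlier outreach program ("Strikingly, 29% of patients receiving organized outreach completed screening within one year"), whose dates are not given.

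**Working it through.** **1. The plan's own figures.** Year count: 2011 - 2006 + 1 = 6, not 7. Seven would need 2005-2011, or 2006-2012, which takes in the start year. The cited earlier window, 2002-2008, is a true seven. The text does not show whether the count or the range is wrong. Aim A's stated power reproduces: with 20,000 at each time point it is about 100% for 39% vs 49% and for 39% vs 44%. No power is stated for the SIR rule.

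**2. Inputs.** From the document: 16,905 patients and 39% up to date in 2011 (Table 1); predicted Year 3 rate 49%; program start 2012. Assumed, because no annual rate before 2011 is given: the secular slope and the year-to-year SD.

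**3. Trend form and date.** Take an assumed slope of 2 points/year and an observed 49%. For 2015 the expected rate is 47.0% (linear), 47.9% (logit-linear) or 49.7% (log-linear), so SIR = 1.043, 1.024 or 0.986. On the linear trend, SIR = 49/45 = 1.089 for 2014, 49/47 = 1.043 for 2015 and 49/49 = 1.000 for 2016.

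**4. Interval method.** Same case, linear, 2015, n = 20,000, yearly SD 1 point. The 95% interval is 1.022-1.063 (Poisson, expected fixed) but 0.931-1.167 once projection error is included.

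**5. Size of the ignored variance.** For a straight line through six years (x = 0 to 5, mean 2.5, sum of squares 17.5), the variance of the projected mean is s² × [1/6 + (x - 2.5)²/17.5]:
- 2014 (x = 8): 0.167 + 30.25/17.5 = 1.90 s²
- 2015 (x = 9): 0.167 + 42.25/17.5 = 2.58 s²
- 2016 (x = 10): 0.167 + 56.25/17.5 = 3.38 s²

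**6. Error with the expected rate fixed, no program effect.** Slope 0.5 point/year. One year's sampling SD is √(0.39 × 0.61/16,905) = 0.375 point. Example for 2014: expected 40.5%, so the Poisson margin is 1.96 × √(0.405/16,905) = 0.96 point. The true SD of observed minus expected is 0.375 × √2.90 = 0.64 point. The ratio is 1.50, an upper-tail error of about 6.7%. Simulation agrees:

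| Year 3 | SD 0 | SD 0.5 | SD 1 |
|---|---|---|---|
| 2014 | 7% | 18% | 30% |
| 2015 | 9% | 21% | 32% |
| 2016 | 11% | 23% | 33% |

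Seven years read as 2005-2011 give 5-6%, 16-18% and 28-30% for 2014-2015. A t-based prediction interval from the same six-year line, t(4 df) × s × √(1 + factor), gives about 2.5% throughout.

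**7. When the direction changes (2014-2015, expected fixed; SD 0, 0.5, 1).**
- Earlier outreach raised 2011 by 1 point: 0.1-0.2%, about 4%, 15%. The 2011 point has weight 0.95 (2014) to 1.10 (2015) in the projection, so the expected rate rises by about that much.
- Yearly rise shrinks by 0.1 point each year: 0%, 1%, 7-10%.
- Yearly rise grows by 0.1 point each year: 74-92%, 65-80%, 59-69%. The prediction interval also fails here: 33-50%, 16-24%, 8-12%.

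**The case against.** This is a secondary analysis, and its result is to be read as supporting evidence. The plan does fix the strata, the standard population, the decision rule and, to within one year, the baseline window. It says the approach was used before and cites a source, which may supply the model and interval; that cannot be checked here. The error figures rest on an assumed slope and yearly SD. Sampling noise alone gives 7-11%; the larger figures need a yearly SD that the document does not give.

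Most of this is fair. A reader might infer that analysts are free to pick the endpoint and the baseline years. The text does not support that: the window is bounded to within one year, and Aim A ties the comparison to the end of Year 3. A reader might also infer that Year 3 falls in 2016, because the sub-study text speaks of participants invited "for the first time late in the 2nd year of the study (currently ongoing" and the footer is dated June 2015. The footer dates the version, not that sentence, so 2016 is only a possibility.

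What stands is that the trend form and interval method are not stated in the plan, the year count contradicts the range, and Year 3 has no date. Citing an earlier use does not adopt a particular model or interval, and it would not resolve six versus seven.

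**Conclusion.** The concern holds as under-specification of the one rule on which Aim A's claim beyond trend depends. It should be corrected. If the expected rate is treated as known and the trend is truly linear, the upper-side error is roughly three to four times nominal from sampling noise alone, and higher with any independent year-to-year variation. These sizes assume n = 16,905, a slope of 0.5 point/year and a six-year line.

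Two tempting readings go too far. The first is that the rule is shown to favor declaring impact. The direction depends on trend shape and on any contamination of the baseline, and the documents give no annual rates to settle either. The second is that the predicted 10-point rise is safe whichever interval is chosen, so that the issue matters only for small effects. That depends on the unknown secular slope, as the figures under the fix show.

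Aim A's chi-square remains valid as a test of change, and the randomized comparisons in Aims B and C are not touched.

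**What to change.** 1. Name the trend model in advance.
2. Judge observed against expected with an interval that includes the projection error of the fitted trend and year-to-year variation, for example a t-based prediction interval with df set by the number of baseline years (4 for six, 5 for seven).
3. Reconcile the seven-year count with 2006-2011, and state the calendar period used as Year 3.
4. State whether the earlier outreach falls in the baseline years and, if so, how those years are handled.

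The change is to SAP wording only; the annual rates are already planned. The price is a wider interval. At SD 0, 0.5 and 1 with six years and 2014-2015, the median half-width is 1.6-1.8, 2.7-3.0 and 4.6-5.1 points, against about 1.0 with the expected rate fixed. Impact is declared less often, by an amount that depends on the slope. For a total rise of 10 points in 2015 with six years, the prediction interval declares impact as follows:

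| Secular slope (points/year) | SD 0 | SD 0.5 | SD 1 |
|---|---|---|---|
| 0.5 | 100% | 100% | 83% |
| 1.2 | 100% | 90% | 50% |
| 2 | 59% | 26% | 12% |

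With the expected rate fixed, the last row would be 91%, 79% and 68%.

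Two limits remain. The prediction interval does not protect against a wrong trend shape. Up-to-date status also carries over between years ("colonoscopy within 10 years, sigmoidoscopy within 5 years, or stool blood test (guaiac FOBT or FIT) within the last year"), so yearly deviations may be correlated; with an assumed AR(1) of 0.5 the prediction interval's error is about 5-6% rather than 2.5%.
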